**Version Date: 5/1/2018** 

arms. We will apply mixed effects logistic regression model to this outcome to account for within-clinic correlation and any unbalanced parent confounding factors. When summarizing parent experience as a continuous variable, we will apply Box-Cox transformation if it is highly skewed and linear mixed effect models to examine the differences in parent experience between control and SPARCK arms.

Aim 3: To characterize the effect of the SPARCK intervention on provider perceptions of barriers to quality vaccine discussions. For Aim 3, providers will be the unit of analysis. We will compare the pre- and post-study proportions of control and SPARCK providers reporting that time, understanding of specific parental vaccine concerns, and knowledge of overall parental vaccine attitudes were significant barriers (defined as 4 or 5 on a 1-5 scale) to quality vaccine discussions. We will use t-tests for an unadjusted analysis of the pre-post differences between control and SPARCK arms and multivariate linear regression for adjusted analyses that control for potential confounding variables such as provider demographic and practice characteristics.

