#### The specific aims of this project are as follows:

Aim 1: Evaluate the impact of the SPARCK intervention on a child's immunization status. We will use a matched-pair, cluster randomized controlled trial design in which we assign up to 30 primary care clinics in the Seattle area and within the Group Health healthcare delivery system in Western Washington to a control arm or the SPARCK arm and enroll 160 vaccine-hesitant parents whose newborns receive health supervision at study clinics.

Aim 2: Assess how parents' ratings of their vaccine discussions with their child's provider change as a function of the SPARCK intervention. This will be accomplished by

Study Title: Screening Parents about Recommended

Care for Kids (SPARCK) Study

Principal Investigator: [name], MPH

Version Date: 5/1/2018

assessing parent visit satisfaction with a questionnaire after their child's 6 month health supervision visit.

Aim 3: Compare pre- and post-study perceptions of barriers to quality vaccine discussions with parents between providers in the SPARCK and control arm. This will be accomplished by having providers complete a survey assessing their perceptions of specific barriers to quality preventive care discussions with parents before the study begins and then again after the study ends.

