**Version Date: 5/1/2018** 

#### **Investigator Help**

## 11. Investigational Plan

## 11.1. Describe the general schema of the study design.

Figure 1. Study Design

This study is a cluster randomized controlled trial. We will pair up to 30 Seattle area primary care clinics and Group Health primary care clinics based upon the number of vaccine doses ordered and enroll and randomize clinics to control and SPARCK arms. We will screen parents for vaccine hesitancy using the Parent Attitudes about Childhood Vaccines Short Form survey (PACV-SF) (Appendix F). Parents in the SPARCK arm of the study will take the intervention survey (which has the PACV embedded in it) to their child's 2 and 6 month visits (Appendix A) whereas parents in the control arm of the study will take a placebo survey about childhood health topics (Appendix B). The results of these surveys will be communicated to the child's provider (Appendices C and D). After the child's 6 month visit, parents in both arms will complete a satisfaction survey about their visit experience (Appendix E). When the child is 8 months of age, we will use an automated clinic immunization database to determine their immunization status. For participants who were lost to follow up (i.e. those who did not have a 6 month appointment, or those who did not have a 2 and 6 month appointment), we will also use Washington State Immunization information System records to determine participant immunization status.

Study Title: Screening Parents about Recommended

Care for Kids (SPARCK) Study

Principal Investigator: [name], MPH

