#### Randomization Method and Blinding

11.4. Describe the randomization method and blinding (if applicable).

Among interested Seattle area primary care practices and 21 Group Health primary care clinics in 5 western Washington counties (King, Snohomish, Pierce, Thurston, and Kitsap), we will pair clinics based upon the number of vaccines doses ordered in the prior year and subsequently enroll and randomize up to 30 to the control and SPARCK intervention arms. We will conceal study arm allocation and describe the study generally as one that seeks to determine the impact of soliciting parent attitudes regarding preventive care topics before health supervision visits on improved health outcomes.

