#### **Analysis Plan and Statistical Methods**

16.1. Outline the data analysis plans relating to each specific aim/objective or research hypothesis mentioned in section 11 above. It should be clear how the analysis results will allow each aim/objective to be answered. The analysis plans for the primary aim should be detailed. Analysis plans for secondary aims may be brief, but must be included. Give the names of specific statistical methods and state which variables will be used with them.

Aim1: To evaluate the effectiveness of the SPARCK intervention in increasing vaccine acceptance. We will conduct an intention-to-treat analysis for Aim 1. Parents will be the unit of analysis. We will examine baseline characteristics among control and SPARCK parents using Pearson's  $\chi 2$  tests (or Fisher's exact tests) for categorical variables and t-tests for continuous variables to assess for any unbalanced confounders between control and SPARCK arms. To compare our primary outcome of percent days underimmunized between control and SPARCK arms, we will apply linear mixed effects regression modeling to the percent days under-immunized with clinic-specific random-effects to account for within-clinic correlation. If unbalanced confounders are detected between arms, they will be adjusted for in the mixed effects models.

Aim 2: To assess how parent-rated experience of the vaccine discussion changes as a function of the SPARCK intervention. For Aim 2, we will use Pearson's χ2 test to compare parent (binary) ratings of their vaccine discussion between control and SPARCK

Study Title: Screening Parents about Recommended

Care for Kids (SPARCK) Study

Principal Investigator: [name], MPH

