## 16.2. Provide a justification for the sample size and power calculations.

Based on preliminary data, children of parents with a positive PACV-SF had a mean percentage of days under-immunized of 27.1% (standard deviation [SD] 33.3) from birth to 8 months of age for 4 vaccines combined (hepatitis B, DTaP, Hib, and IPV). To be able to detect with adequate power (90%) a decrease in under-immunization of 30 days per vaccine—a decrease that has the potential to be clinical meaningful since it equals the 1 month recommended interval a parent has before their child is considered late for a vaccination dose—we need to enroll 160 parent/newborn pairs total, with 80 per arm and 10 at each of the 16 study clinics (assuming an  $\alpha$  of 0.05 and an intraclass correlation coefficient for within-clinic correlation of 0.02).

In our original calculation, we assumed 80% of GH parents would be reached, a conservative estimate of a 20% prevalence of GH parents who will have a positive PACV-SF, 10% of VHPs who fail to meet other study eligibility requirements, 25% of VHPs who do not agree to participate (unpublished data), a 10% attrition rate over the course of the study, and 70% who remain continuous GH members, resulting in the need to approach 2400 parents to reach our sample size goal. From 2010 – 2012, there was an average of 2679 GH births per year in the 5 Washington State counties from which we will recruit parents. Reaching our sample size goal should therefore be feasible given our designated 15 month recruitment period. However, we now know that the vaccine hesitancy rate at GH is about 5%. Therefore, we need to screen approximately 3500 parents to reach the desired sample size goals of 160.

For Aim 2, we will have 80% power with a sample size of 160 parents to detect a 17% increase in the proportion of parents who rate their visit highly, assuming a baseline proportion of 72%.  For Aim 3, we will have 80% power to detect a 14% pre-post difference in the proportion of providers who perceive time as a barrier to quality vaccine discussions between control (1% pre-post difference) and SPARCK arms (15% pre-post difference), assuming a baseline proportion of 62% and 56 providers in each arm.

Study Title: Screening Parents about Recommended

Care for Kids (SPARCK) Study

Principal Investigator: [name], MPH

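### Clinics are randomised, but the Aim 3 t-test and regression treat providers as independent; the Aim 2 and Aim 3 power statements apply no stated ICC

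*Combined protocol and SAP*

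**What the plan says.** The design is clustered throughout. Section 1.1, Aim 1: "We will use a matched-pair, cluster randomized controlled trial design in which we assign up to 30 primary care clinics". Section 11.1 says the study will "enroll and randomize clinics to control and SPARCK arms", and section 11.4 describes the matching: "we will pair clinics based upon the number of vaccines doses ordered in the prior year".

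Section 16.1 then handles the three aims differently.

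- **Aim 1:** a linear mixed model "with clinic-specific random-effects to account for within-clinic correlation".
- **Aim 2:** a Pearson chi-square test of the binary rating between arms, and then: "We will apply mixed effects logistic regression model to this outcome to account for within-clinic correlation". Linear mixed models are used if the rating is summarised as continuous.
- **Aim 3:** "For Aim 3, providers will be the unit of analysis". A barrier counts as significant if it is rated 4 or 5 on a five-point scale. On method: "We will use t-tests for an unadjusted analysis of the pre-post differences between control and SPARCK arms and multivariate linear regression for adjusted analyses". The adjustment variables are features of the provider and the practice, offered as possible confounders.

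No random effect, GEE or cluster-robust variance is named for Aim 3 there or elsewhere.

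In section 16.2 the Aim 1 calculation assumes "an intraclass correlation coefficient for within-clinic correlation of 0.02", with 10 parents in each of 16 clinics. The Aim 2 sentence gives 80% power, 160 parents, a 72% baseline and a 17-point increase. The Aim 3 sentence gives 80% power, 56 providers per arm, and pre-post differences of 1% (control) and 15% (SPARCK). Neither sentence states an ICC.

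**The concern.** Providers in one clinic share an allocation, a patient population and a working environment, so their changes in perception may be correlated. A provider-level t-test or ordinary regression takes its standard error from the number of providers. Any clinic-to-clinic variation in change is then partly read as a difference between arms. Subtracting the baseline rating does not solve this. It removes what is constant in a clinic over time, but not clinic-level differences in how much providers change.

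At stake is the error rate and interval width of one of the three stated aims. A linked question is whether the quoted 80% power for Aims 2 and 3 allows for clustering.

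**Working it through.** **Step 1. Size of the Aim 3 test as written.** Inputs: 56 providers per arm, so 112 in all (section 16.2); 16 clinics (section 16.2) or up to 30 (sections 1.1, 11.1, 11.4). Assumptions: equal clinic sizes, normal approximation, two-sided 5%. The ICC for provider change is not given, so it is varied.

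DE = 1 + (m − 1) × ICC, and actual size = 2 × [1 − Φ(1.96/√DE)].

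| Clinics | m | ICC 0.02 | ICC 0.05 | ICC 0.10 |
|---|---|---|---|---|
| 16 | 112/16 = 7 | DE 1.12, 6.4% | DE 1.30, 8.6% | DE 1.60, 12.1% |
| 30 | 112/30 = 3.73 | DE 1.055, 5.6% | DE 1.137, 6.6% | DE 1.273, 8.2% |

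More respondents per clinic make it worse. Section 2.1 expects about 200 + 85 = 285 providers. If all completed both surveys in 16 clinics, m = 17.8, DE = 1.336 and size is 9.0% at ICC 0.02.

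Simulation agrees (8,000 runs per scenario, normal change scores, clinics randomised within pairs, no true effect). With 112 providers the provider-level t-test rejected in 6.2%, 8.6% and 12.6% of runs (16 clinics) and 6.0%, 6.6% and 8.2% (30). A t-test on clinic means with df = clinics − 2 rejected in 4.9% to 5.5%. A further simulation with three-valued changes (−1, 0, +1) also kept clinic-level t-tests near 5%.

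**Step 2. The plan's own power figures.** Two independent proportions, two-sided 5% (assumed), no design effect.

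- Aim 2, 72% v 89%, 80 per arm. Unpooled: 0.17/√[(0.72×0.28 + 0.89×0.11)/80] = 2.78; Φ(2.78 − 1.96) gives 79.3%. Pooled null variance gives 78.0%.
- Aim 3, 1% v 15%, 56 per arm. Unpooled: 0.14/√[(0.01×0.99 + 0.15×0.85)/56] = 2.83; Φ(2.83 − 1.96) gives 80.7%. Pooled gives 78.7%.

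Both are close to the stated 80%. The Aim 3 match is not unique: an arcsine formula gives 88.3% with independence and 80.7% with ICC 0.04 and m = 7 (DE 1.24).

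**Step 3. Power with the Aim 1 ICC of 0.02 carried over (an assumption).** Replace n by n/DE.

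- Aim 2: 16 clinics, m = 10, DE 1.18, n = 67.8: 70.9% to 72.5%. With 30 clinics, m = 5.33, DE 1.087: 74.5% to 76.0%.
- Aim 3: 16 clinics, DE 1.12, n = 50: 74.0% to 76.1%. With 30 clinics, DE 1.055: 76.5% to 78.6%.

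**Step 4. Why the Aim 3 figures are ceilings.** A provider's change in a binary barrier is −1, 0 or +1. The variance 0.01×0.99 + 0.15×0.85 = 0.1374 is right only if nobody moves against the net direction. Suppose, for illustration, that 5% in each arm do, with the same net changes. Control variance is 0.06 + 0.05 − 0.01² = 0.1099, SPARCK variance is 0.20 + 0.05 − 0.15² = 0.2275, and the sum is 0.3374. At 56 per arm, with no clustering at all, 0.14/√(0.3374/56) = 1.80 and power is about 44%.

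**The case against.** Four replies deserve weight.

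- *Practice characteristics are already in the adjusted model.* They enter as measured confounders. They do not model the remaining within-clinic correlation, and the unadjusted t-test does not contain them.
- *The excess is modest.* This stands in part. At the only ICC the documents state (0.02, used for the parent-level primary outcome) and the planned 112 providers, size is 5.6% to 6.4%. The larger figures need a higher ICC or more providers per clinic.
- *Aim 2 is covered.* Its mixed model handles clustering, but the plan also lists an unclustered chi-square test and does not say which result governs.
- *Section 16.2 does give a cluster layout.* It does: the 160 parents of Aim 2 are the same parents placed 10 to a clinic in 16 clinics. What is unstated is whether that layout and ICC were used for Aim 2.

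A reader might infer that the Aim 2 and Aim 3 powers were certainly computed without clustering. The documents show no formula, and for Aim 3 a clustered arcsine calculation fits equally well, so this is only probable.

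A reader might also infer that enrolling about 285 providers makes Aim 3 power safe. That does not follow. At 142.5 per arm, ICC 0.02 and 5% reversals, 0.14/√(0.3374 × 1.336/142.5) = 2.49, giving about 70% in 16 clinics; with DE 1.17 in 30 clinics it is about 76%. The documents give no variance for individual change that would settle the matter.

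**Conclusion.** The Aim 3 analysis does not match the randomisation. As written it is anti-conservative whenever provider change varies between clinics. The direction is certain for any positive ICC; the size is not, because no ICC for provider change is given. Over the assumed range of 0.02 to 0.10, with 112 providers in equal-sized clinics, the actual size is 6.4% to 12.1% in 16 clinics and 5.6% to 8.2% in 30.

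The power point is held with less confidence. Clustering was probably left out. If so, at ICC 0.02 and 16 clinics, Aim 2 power is about 71% to 73%, and Aim 3 power is at most about 74% to 76%.

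Nothing here reaches the primary analysis, which has clinic random effects. It also does not show that Aim 2 inference is invalid, provided the mixed model is the governing analysis. Both aims are secondary, so this should be fixed but does not threaten the trial's main conclusion.

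**What to change.** - **Aim 3 regression:** keep the regression of pre-post change and add a clinic random effect with small-sample degrees of freedom, or use a small-sample cluster-robust variance.
- **Aim 3 unadjusted test:** replace the provider-level t-test with a t-test on clinic mean changes, df = clinics − 2, or label the provider-level test descriptive only. If the matched pairs are kept in the analysis, say so in advance and use df = pairs − 1.
- **Aim 2:** state that inference rests on the mixed model and that the chi-square test is descriptive.
- **Power:** restate both figures with the ICC, the number of clinics and the expected number analysed. For Aim 3, count providers who complete both surveys and give the assumed variance of individual change.

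The cost is wording and one model term, on data already to be collected. Aim 3 intervals widen to their proper length. At 112 providers and ICC 0.02, the ratio t(0.975, df) × √DE / t(0.975, 110) is 1.145 with 16 clinics (df 14) and 1.062 with 30 (df 28), so about 15% and 6% wider with the unpaired clinic-level test.

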## 16.2. Provide a justification for the sample size and power calculations.

Based on preliminary data, children of parents with a positive PACV-SF had a mean percentage of days under-immunized of 27.1% (standard deviation [SD] 33.3) from birth to 8 months of age for 4 vaccines combined (hepatitis B, DTaP, Hib, and IPV). To be able to detect with adequate power (90%) a decrease in under-immunization of 30 days per vaccine—a decrease that has the potential to be clinical meaningful since it equals the 1 month recommended interval a parent has before their child is considered late for a vaccination dose—we need to enroll 160 parent/newborn pairs total, with 80 per arm and 10 at each of the 16 study clinics (assuming an  $\alpha$  of 0.05 and an intraclass correlation coefficient for within-clinic correlation of 0.02).

In our original calculation, we assumed 80% of GH parents would be reached, a conservative estimate of a 20% prevalence of GH parents who will have a positive PACV-SF, 10% of VHPs who fail to meet other study eligibility requirements, 25% of VHPs who do not agree to participate (unpublished data), a 10% attrition rate over the course of the study, and 70% who remain continuous GH members, resulting in the need to approach 2400 parents to reach our sample size goal. From 2010 – 2012, there was an average of 2679 GH births per year in the 5 Washington State counties from which we will recruit parents. Reaching our sample size goal should therefore be feasible given our designated 15 month recruitment period. However, we now know that the vaccine hesitancy rate at GH is about 5%. Therefore, we need to screen approximately 3500 parents to reach the desired sample size goals of 160.

For Aim 2, we will have 80% power with a sample size of 160 parents to detect a 17% increase in the proportion of parents who rate their visit highly, assuming a baseline proportion of 72%.  For Aim 3, we will have 80% power to detect a 14% pre-post difference in the proportion of providers who perceive time as a barrier to quality vaccine discussions between control (1% pre-post difference) and SPARCK arms (15% pre-post difference), assuming a baseline proportion of 62% and 56 providers in each arm.

Study Title: Screening Parents about Recommended

Care for Kids (SPARCK) Study

Principal Investigator: [name], MPH

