**Version Date: 5/1/2018** 

17.6. Describe who (individual or group) will periodically review the study conduct and data to assess safety for current or future participants. Include what data will be reviewed and the frequency of the review.

Drs. [name] (PI), [name] (co-investigator) and [name] (co-investigator) will monitor the progress of the trial through quarterly assessments of data quality and timeliness, participant recruitment, accrual and retention, participant risk versus benefit, and other factors that could affect study outcomes. We will make quarterly determinations regarding continuation or conclusion of the trial based on these assessments.

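### The revised figure of about 3500 parents to screen does not follow from the recruitment rates the plan states; applied throughout, those rates give about 118 enrolled from 3500, or about 4740 to screen for 160.

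*Combined protocol and SAP*

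**What the plan says.** Section 16.2 sets the target: "we need to enroll 160 parent/newborn pairs total".

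It then describes a first recruitment calculation for Group Health (GH): 80% of parents reached, 20% screening positive for hesitancy, "10% of VHPs who fail to meet other study eligibility requirements, 25% of VHPs who do not agree to participate", 10% attrition and 70% remaining GH members throughout. This gives 2400 parents to approach. On supply, it says that "there was an average of 2679 GH births per year in the 5 Washington State counties" in 2010 to 2012, and infers: "Reaching our sample size goal should therefore be feasible given our designated 15 month recruitment period".

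The next sentence changes one input: "However, we now know that the vaccine hesitancy rate at GH is about 5" percent. The section then concludes: "Therefore, we need to screen approximately 3500 parents to reach the desired sample size goals of 160". It gives no further calculation and does not return to the 15-month statement.

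Two other places bear on this. Section 2.1 still lists about 2400 parents screened and 160 enrolled. Section 11.4 shows that GH is not the only source of parents, since clinics are drawn from "Among interested Seattle area primary care practices and 21 Group Health primary care clinics in 5 western Washington counties".

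**The concern.** Hesitancy falls to a quarter of its assumed value, yet the stated number rises only from 2400 to 3500, a factor of 1.46. The sentence is introduced as a consequence of the new rate, so a reader expects to be able to derive it from the rates on the page.

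What is at stake is feasibility and planning. The number to screen sets staffing, the number of clinics and the length of recruitment. If it is too low, the trial risks enrolling fewer than 160 or recruiting for longer than planned. It does not affect the endpoint, the error rate or the method of analysis.

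**Working it through.** **Inputs (all from section 16.2).** Target 160. Reach 80%. Hesitancy 20%, then about 5% at GH. Ineligible for other reasons 10%. Refusal 25%. Attrition 10%. Continuous GH membership 70%. GH births 2679 per year. Recruitment period 15 months.

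**Method.** Number needed = 160 / (product of the rates that apply). Expected yield = number × the same product.

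**1. Reproduce the plan's first figure.**
- All stated rates: 160 / (0.80 × 0.20 × 0.90 × 0.75 × 0.90 × 0.70) = 160 / 0.06804 = 2352, which agrees with the stated 2400.
- Stopping at enrolment: 160 / (0.80 × 0.20 × 0.90 × 0.75) = 160 / 0.108 = 1481, which does not.

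So the multiplication is the plan's own method, and 2400 is obtained only if 160 counts parents who are retained and remain GH members.

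**2. Apply the revised hesitancy rate.** Take the 3500 as parents already reached, and count enrolment only. Both choices favour the plan.
- Hesitant: 3500 × 0.05 = 175
- Eligible: 175 × 0.90 = 157.5
- Consenting: 157.5 × 0.75 = 118.1, which is 74% of 160
- Number to screen for 160: 160 / (0.05 × 0.90 × 0.75) = 160 / 0.03375 = 4741
- Share of the 175 who would have to enrol for 3500 to suffice: 160 / 175 = 91.4%, against 0.90 × 0.75 = 67.5% stated

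**3. Allow for rounding in the 5%.**

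| Hesitancy | Enrolled from 3500 | To screen for 160 |
|---|---|---|
| 4.5% | 106 | 5267 |
| 5.0% | 118 | 4741 |
| 5.5% | 130 | 4310 |

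**4. Look for a route to 3500.**
- Combining 5% with every subset of the other five rates, only a single 10% loss comes within 3% of 3500: 160 / (0.05 × 0.90) = 3556. That leaves out the 25% refusal.
- Hesitancy alone gives 160 / 0.05 = 3200.
- With the 10% and 25% kept, 3500 suffices if overall hesitancy is 160 / (3500 × 0.675) = 6.77%.
- Share of screening that non-GH clinics would then have to supply, as an assumption about their unstated rate q, is (0.0677 − 0.05) / (q − 0.05): about 35% at q = 10%, 18% at q = 15%, 12% at q = 20%.

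**5. Check the 15-month supply from GH at 5%, 10% and 25%.**
- Births in 15 months: 2679 × 15/12 = 3349, fewer than 3500.
- All screened: 3349 × 0.03375 = 113 enrolled.
- At 80% reach: 0.80 × 3349 = 2679; 2679 × 0.03375 = 90 enrolled.
- Counting also infants up to 2 months old at opening (17 months of births, all screened): 2679 × 17/12 = 3795; × 0.03375 = 128 enrolled.
- Remainder for other clinics: 160 − 128 = 32, up to 160 − 90 = 70.
- Most favourable case, 5.5% with 17 months of births all screened: 3795 × 0.055 × 0.675 = 141, still below 160.

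**The case against.** The strongest reply is that the figure of 118 mixes inputs the plan does not mix. The 5% is stated for GH, while 3500 is the total for a trial that also recruits elsewhere. The 10% and 25% belong to the first calculation and are not restated; since the new hesitancy rate appears to come from experience, consent may have been better than assumed too. The unit also shifts from parents approached (2400) to parents screened (3500).

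Much of this stands. A higher rate at the other clinics could explain 3500: the shares in step 4 are not implausible, and the plan once regarded 20% as a cautious value even for GH. So 118 is a conditional result, not a forecast. But the plan gives no rate, births or share of screening for those clinics, and no revised consent rate, so the stated conclusion still lacks a stated basis.

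A second reply is that little depends on 3500. This is partly right. A reader might infer that 3500 is the plan's evidence for recruiting in 15 months; in fact that sentence comes earlier and rests on 2400. A reader might also infer that trial continuation hangs on 3500, because section 17.6 says "We will make quarterly determinations regarding continuation or conclusion of the trial based on these assessments". Those assessments include recruitment and accrual among several factors, but no rule there refers to the screening number.

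**Conclusion.** The concern holds in conditional form. About 3500 cannot be derived from the rates the plan states. If 5%, 10% and 25% apply throughout, 3500 screened enrols about 118 (106 to 130 for hesitancy of 4.5% to 5.5%), and 160 enrolled needs about 4740 (5270 to 4310). The two routes that come close, omitting refusal or assuming about 6.8% hesitancy overall, are not stated.

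The 15-month sentence was not redone after the change. At the stated rates GH alone would enrol roughly 90 to 128, so about 32 to 70 of the 160 would have to come from clinics whose births and rates are not given. Section 2.1 still carries the superseded 2400.

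Three stronger readings are not supported:
- That the trial will enrol only 118. This would need the GH rate and the first calculation's losses to hold at every clinic, which the plan does not say.
- That the correct number is 160 / (0.05 × 0.80 × 0.90 × 0.75 × 0.90 × 0.70) = 9406. This carries GH reach and membership over to all clinics and counts approached rather than screened parents.
- That at least 47 must come from outside GH (160 − 113). Counting infants already born at opening lowers the gap to 32.

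This is a planning and consistency error that should be corrected. It does not touch the validity of the analysis.

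**What to change.** - In section 16.2, replace the single figure with a stated funnel giving hesitancy, eligibility and consent rates separately for GH and other clinics, and show the multiplication. If 5%, 10% and 25% apply throughout, the result is about 4740. If other rates have since been observed, state them and their source.
- Say whether 160 means enrolled or retained. The text says enrolled, but 2400 is reproduced only if retained; section 11.10 says attrition is allowed for in the sample size, and section 16.3 excludes missing data. If 160 means retained after 10% attrition, the same rates give 160 / (0.05 × 0.675 × 0.90) = 5267.
- Restate the 15-month feasibility sentence against the recomputed number, including the expected number of infants at non-GH clinics.
- Make the number screened in section 2.1 agree.

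The cost is wording and recomputation in two sections. Rates by clinic type have to be stated, and the feasibility statement becomes less favourable. The target of 160, the endpoint and the analysis stay as they are.

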**Version Date: 5/1/2018** 

16.3. **Describe how missing data will be handled.** Missing data will be excluded from analysis.

- 16.4. Describe plans for interim analysis and early stopping rules (if applicable). N/A
- 16.5. Describe under what circumstances will un-blinding occur and the procedures to do so (if applicable). N/A

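### Aim 3's 80% power with 56 providers per arm rests on the smallest possible variance of the pre-post change, so it is a best case rather than an expected value

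*Combined protocol and SAP*

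**What the plan says.** Section 16.1 sets out the Aim 3 analysis. "For Aim 3, providers will be the unit of analysis". Three perceived barriers (time, understanding of specific parental concerns, knowledge of overall attitudes) are each reduced to yes or no according to whether they "were significant barriers (defined as 4 or 5 on a 1-5 scale) to quality vaccine discussions". The test is then named: "We will use t-tests for an unadjusted analysis of the pre-post differences between control and SPARCK arms". A multivariable linear regression follows for adjusted results. It lists provider demographics and practice characteristics as possible covariates, but not the provider's own baseline answer. Aims 1 and 2 carry a clinic term; none is named for Aim 3.

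Section 16.2 gives the power for the time barrier: "we will have 80% power to detect a 14% pre-post difference in the proportion of providers who perceive time as a barrier". The 14 points are the gap between a 1% change in control and a 15% change in SPARCK, "assuming a baseline proportion of 62% and 56 providers in each arm". It states no standard deviation for the change, no pre-post correlation and no rate of switching in either direction.

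Three other sections bear on the point. Section 5.3 puts provider participation at about 15 months. Section 16.3 says "Missing data will be excluded from analysis", so only providers with both surveys contribute. Section 2.1 expects about 200 Group Health and 85 other providers to enrol.

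**The concern.** A provider who answers a yes/no item twice has a change of -1, 0 or +1. The spread of that change depends on everyone who switches in either direction, not only on the net movement. Two providers who switch in opposite directions leave the net change where it was but add to the variance. The planning figure seems to have counted only the net movement.

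The sentence will matter when the result is read. If Aim 3 shows no difference, a reader who trusts 80% power will take that as fair evidence that the intervention does not shift perceived barriers by 14 points. If true power at that sample size is well below 80%, the inference is weaker than it looks.

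**Working it through.** **Inputs.** From 16.2: net changes of 0.01 (control) and 0.15 (SPARCK), difference 0.14; baseline 0.62; 56 per arm. From 16.1: two-sample t-test on provider differences. Alpha of 0.05 is stated in 16.2 for Aim 1 and is assumed to carry over, two-sided. A fall in the proportion is assumed (0.62 to 0.61 or 0.47); a rise gives similar power.

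**Step 1: reproduce the 80%.** Treat 0.01 and 0.15 as plain proportions.
- Variances: 0.01 × 0.99 = 0.0099 and 0.15 × 0.85 = 0.1275.
- Standard error: √((0.0099 + 0.1275)/56) = 0.0495.
- Ratio: 0.14/0.0495 = 2.83.
- Power: 80.0% by noncentral t on 110 df, 80.7% by the unpooled normal approximation, 78.7% by the pooled formula.
- The unpooled normal formula needs 55.02 per arm for 80% power, which rounds up to the plan's 56.

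The 62% was not used. Comparing follow-up proportions alone (61% against 47%) gives 32%, so that route does not produce the stated figure.

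**Step 2: variance of the planned quantity.** For a difference D in {-1, 0, +1},

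Var(D) = P(up) + P(down) − (P(down) − P(up))².

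For a fixed net change this is smallest when one of P(up) and P(down) is zero. It then equals net − net²: 0.01 − 0.0001 = 0.0099 and 0.15 − 0.0225 = 0.1275. These are exactly the Step 1 variances. The plan's figure therefore assumes that 1% of controls and 15% of SPARCK providers change their answer between surveys, all in one direction.

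**Step 3: allow switching both ways.** Let a further share c switch in each direction in both arms. Each variance rises by 2c and the net changes stay the same. With 56 per arm:

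| c (assumed) | Var control | Var SPARCK | Power (noncentral t) | n per arm for 80% (normal) |
|---|---|---|---|---|
| 0 | 0.0099 | 0.1275 | 80% | 56 |
| 1% | 0.0299 | 0.1475 | 69% | about 71 |
| 2.5% | 0.0599 | 0.1775 | 57% | about 95 |
| 5% | 0.1099 | 0.2275 | 43% | about 135 |
| 10% | 0.2099 | 0.3275 | 29% | about 215 |
| 15% | 0.3099 | 0.4275 | 23% | about 295 |

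Simulated t-tests (20,000 runs) gave 43%, 30% and 23% at c = 5%, 10% and 15%. At c = 0 the simulation gave 86%, because the approximation is rough when barely one control provider is expected to change (56 × 0.01 = 0.56). That departure is confined to the no-switching case.

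**Step 4: the same by pre-post correlation.** With phi the correlation between the two yes/no answers,

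Var(D) = p0(1−p0) + p1(1−p1) − 2·phi·√(p0(1−p0)·p1(1−p1)),

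with p0 = 0.62 and p1 = 0.61 or 0.47. Power at 56 per arm is 24% at phi 0.3, 32% at 0.5 and 49% at 0.7. A single phi shared by both arms cannot go much higher: in SPARCK the margins cap it at √(0.47 × 0.38/(0.62 × 0.53)) = 0.74. The plan's 80% corresponds to the maximum phi in each arm: 0.74 in SPARCK and √(0.61 × 0.38/(0.62 × 0.39)) = 0.98 in control.

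**Step 5: the provider count in section 2.1.** 200 + 85 = 285, or about 142 per arm if split evenly. If all complete both surveys, power is 93% at c = 2.5%, 82% at 5%, 62% at 10% and 49% at 15%. At 100 per arm it is 82%, 67%, 48% and 37%.

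Clinic correlation is left out throughout. The 0.02 in 16.2 belongs to the Aim 1 parent calculation.

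**The case against.** The strongest reply is that the figure reproduces, so it is not a slip of arithmetic. That is right: the fault lies in an unstated and most favourable variance assumption.

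A reader might go further and infer that realistic power is some low figure such as 20% to 45%. The documents do not support that. They contain no test-retest, switching or correlation figure, and modest instability gives more (57% at 2.5% each way, 49% at phi 0.7). Nor does the 62% baseline show that many providers sit close to the cut. It is the share assumed to be at or above it, and says nothing about how many answer 3 or 4.

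A reader might also infer that the trial has little chance of detecting an effect on Aim 3. Section 2.1 stands against that: with about 142 paired providers per arm, power reaches about 82% at 5% switching each way. This does not rescue the sentence in 16.2, which is tied to 56 per arm, and full completion of both surveys is itself an assumption.

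Finally, the share of providers who call something a significant barrier is a legitimate and readable endpoint. Correcting the power sentence does not require replacing it with the 1-5 score. Aim 3 is one of two secondary objectives in 9.2, the trial is sized on Aim 1, and the 16.1 template allows brief plans for secondary aims. This lowers the priority but does not make the 80% right.

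**Conclusion.** The point holds for the power sentence. On the plan's own method, 80% is the best-case value for the t-test named in 16.1 with 56 providers per arm, and any switching against the net direction lowers it. That conclusion follows from the stated inputs, with two-sided alpha of 0.05 assumed.

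The size of the shortfall depends on assumptions that the documents do not settle: from 69% at 1% extra switching each way to 23% at 15%, or about 24% to 49% for phi 0.3 to 0.7. Clinic correlation would be expected to lower these further, and more paired providers than 56 per arm would raise them. Severity is moderate: no primary conclusion or recruitment target depends on the sentence.

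**What to change.** 1. **Section 16.2.** Replace the 80% statement with power, or a detectable difference, computed from the variance of the pre-post change. State the assumed switching rate or pre-post correlation and show a range. By the normal formula, the difference detectable with 80% power at 56 per arm is 2.80 × √((0.1099 + 0.2275)/56) = about 22 points at 5% switching each way, and 2.80 × √((0.2099 + 0.3275)/56) = about 27 points at 10%.
2. **Section 16.2 with 2.1.** Reconcile 56 per arm with about 285 expected providers, and state the assumed share who complete both surveys. Say whether clinic correlation is included.
3. **Section 16.1.** Adjust the follow-up response for the provider's own baseline response, which is already collected. In one simulation (latent correlation 0.5, an assumed split of ratings, 56 per arm) this raised power for the yes/no item from 26% to 35%. Keep the proportion answering 4 or 5 as the endpoint. An analysis of the full 1-5 rating may be added as supportive.

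The cost is a change of wording and probably a less favourable power statement. No new data, visits or participants are needed.
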